5.2 Description of study evaluations

1. EMR data pulls and manual chart reviews: EMR data and manual chart review data will be collected from two cohorts of patients: (1) patients attending clinics after implementation (post- implementation cohort) and (2) patients attending clinics before implementation (pre-implementation). For the pre-implementation cohort, data will be collected over a six-month period. For the post-implementation cohort, data will be collected from the time of study implementation until the end of the study.
2. Pathway Platform data and analytics: Data on patient outcomes and Pathway Platform usage will be collected throughout the study starting at day 1 and ending on the final day of the patient's participation (i.e. 6 months, common study end date or patient withdrawl). Similarly, data on report usage by care team will be collected throughout the study.
3. Educational resource center analytics: The number of times material in the resource center is viewed will be recorded between day 1 and the end of the study.

6. SAFETY ASSESSMENTS

6.1 Adverse Events Related to the Pathway Platform

No adverse events (AEs) are expected in this minimal risk study related to the Pathway Platform; however, all serious adverse events (SAEs) that are spontaneously reported during the study period will be collected.

A SAE is defined as an adverse event, reported during the implementation study of the Pathway Platform, in the view of either the investigator or sponsor, results in any of the following outcomes:

- a. Death
- b. Life-threatening adverse event
- c. Inpatient hospitalization or prolongation of existing hospitalization (for > 24 hours)
- d. Persistent or significant incapacity or substantial disruption of the ability to conduct normal life functions
- e. Congenital anomaly/birth defect.

f. Important medical events that may not result in death, be life-threatening or require hospitalization may be considered serious when, based upon appropriate medical judgment, they may jeopardize the participant and may require medical or surgical intervention to prevent one of the outcomes listed in this definition.

The following information will be collected for any SAE that is reported:

- Event details
- Start and stop date
- Frequency
- Intensity
- Investigator's opinion of the causal relationship to study procedure(s), including the details of the suspected procedure
- Outcome of event
- Severity

Causality to study procedures will be determined for all SAEs and deemed "related" or "not related" to the intervention. Severity will be assessed as mild (event is transient and easily tolerated by the subject), moderate (event causes the subject discomfort and interrupts the subjects' usual activities), or severe (event causes considerable interference with the subject's usual activities). The start date of the SAE is the date that the first signs or symptoms were noted. The stop date is the date on which the subject recovered, the event resolved, or the subject died.

All SAEs, along with the information bulleted above, will be compiled and included in the final study report. SAEs will be reported to Takeda within 24 hours of becoming aware of the event.

6.2 Change in Participant Suicidal Ideation

Patients using the Pathway Platform will answer biweekly PHQ-9 surveys, during which Item 9 asks about the frequency of suicidal ideation. It is possible that a patient will report a change in suicidal ideation in the course of responding to this question. In the event that a patient responds affirmatively to this question, the patient will receive a pop-up notification that s/he should contact his/her health care provider or emergency services immediately. This instruction is what is given in routine clinical practice. The

data from the Pathway Platform is not monitored in real time by care teams. Patients will be informed via consent that the information provided to the Pathway Platform is not directly or continuously monitored. As an additional item of note, data from the Pathway Platform may be delayed and/or not received by the EMR if device is unable to transmit data.

This information will also be included in the patient consent and will be explained to the patient by the Care Team during the consent process.

7. INTERVENTION DISCONTINUATION

Patients are not required to use the Pathway Platform and can choose to discontinue at any time. Adherence to use will be tracked and reported for analytical purposes.

8. STATISTICAL CONSIDERATIONS

8.1 General Design and Hypothesis

The following hypotheses will be examined:

Primary hypothesis: PHQ-9 utilization will be greater after implementation compared to before implementation of the Pathway Platform.

Secondary hypothesis: Provider processes and patient depression related outcomes will have greater improvements in patient outcomes after implementation of the App compared to previous practice patterns.

8.2 Sample size and randomization

The primary outcome for this study is PHQ-9 utilization. Assuming 75% PHQ-9 utilization prior to implementation of the Pathway Platform and 90% PHQ-9 utilization after implementation of the Pathway Platform, we will need 100 patients per group, for a total of 200 patients, assuming 80% power and a 2-sided alpha of 0.05 using Pearson chi square test for two independent proportions. To allow for subgroup analyses the sample will include 200 patients per group, for a total of 400 patients; 200 patients will comprise the “post-implementation” cohort and 200 will comprise the “pre-implementation” cohort. **Table 2** presents additional sample size calculations based on different assumptions of PHQ-9 utilization.

Table 2: Sample size calculations based on different assumptions of PHQ-9 utilization, alpha = 0.05, Power = 80%.
--

PHQ-9 utilization pre-implementation	PHQ-9 in Pathway post-implementation	N patients per group
75%	80%	1,094 per group
75%	90%	100 per group
75%	95%	49 per group
50%	65%	170 per group
50%	80%	30 per group
50%	90%	20 per group

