3.1 Performance among participating clinics post-implementation

The Pathway Platform will be implemented in up to 20 primary care sites within the Advocate Aurora Health system and enroll a total of 200 patients for six-month duration. The visit where the patient has been onboarded to the Pathway Platform will be the enrollment visit (Figure 1). During the post- implementation period, data on patient outcomes will be collected through the Pathway Platform. At the end of the study an electronic and manual chart review for patients using the Pathway Platform will be conducted among participating clinics and performance related to measurement-based care, shared decision making and collaborative care, where applicable, will be assessed over the post-implementation period.

3.2 Retrospective Assessment: pre-implementation performance at the clinic level (before Pathway Platform implementation)

To assess Advocate's primary care sites performance pre-implementation, an electronic and manual chart review will be conducted from the same Advocate primary care clinics participating in the implementation study. Patients with a clinic visit at least 6 months prior to implementation (index visit) of the Pathway Platform and meeting the inclusion criteria for enrollment in the study, will be included in this analysis (figure 1). Patient history will be evaluated for three months prior to index visit to confirm eligibility. The goal is to capture patients with a new start, dose adjustment or switch of an antidepressant medication 6 months prior to the implementation index date (three-month inclusion window for patient identification). Six months of patient history will be “retrospectively” collected for this baseline patient cohort to assess the primary outcome, defined as PHQ-9 utilization, and other secondary outcomes outlined in the protocol. This analysis will serve as the comparison control for the primary and secondary outcomes to compare performance at the same clinics pre and post-implementation of the Pathway Platform. Depending on the number of eligible patients identified per site (20 per site), group level matching for age and sex may be conducted. The primary endpoint will be the proportion of patients with at least 2 PHQ-9 scores.

Figure 1: Study schematic

* Primary and secondary outcomes will be evaluated at 6 months, data collected beyond 6 months will be used for exploratory analysis

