4.4.3 Educational Scaffolding

An online Educational training program was developed using evidence-based medicine building

on measurement-based care and shared-decision making concepts as they relate to depression management. Educational material describes how the Pathway Platform can help care team members in clinical processes related to these process improvement measures. In clinics using a collaborative care model additional education material specific to this care model is provided. Educational material housed in an online resource center which includes reading material, presentations, and videos. Additionally, up to three audit and feedback sessions will be conducted for each participating clinic. The objectives of audit and feedback sessions are to benchmark performance measures, including shared decision making, reflect on current clinical practice and improvement strategies, and setting team-based action plans. Care team members who manage depression must complete specific training before they are able to enroll patients and begin using the Pathway Platform.

A training manual was also developed for patients. The manual describes the Pathway Platform functionality, as well as, how to use and interpret the data collected.

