8.4 Data analysis

For primary and secondary hypothesis testing, process measures, patient clinical outcomes, and health care resource utilization will be compared pre- and post- implementation of the Pathway Platform.

Additional patient reported outcomes will be compared among patients using the Pathway Platform only at baseline and end of study. For pre-implementation, outcomes will be assessed among patients who visited one of the study clinics at least once over the pre-implementation study period and were eligible to use the Pathway Platform, if it had been available. For the post-implementation period, the Pathway Platform will be the data source for paired t-test analysis, assessing change in continuous variables including PHQ-9 scores. Categorical outcomes will be presented as proportions and compared using Pearson Chi2 test. Continuous outcomes will be assessed for normality and presented as means and standard deviations (SD) or medians and interquartile ranges (IQR); continuous outcomes will be compared using Student's t test for independent groups. Two-tailed tests using a significance threshold of $p < 0.05$ will be used for all tests.

Exploratory outcomes: will be described among patients attending the pathway platform clinics only and will be compared between baseline, 6-month and extended follow up. Change in these outcomes overtime, including utilization analytics will also be explored. Categorical outcomes will be presented as proportions and compared using McNemars' test. Continuous outcomes will be assessed for normality and presented as means and standard deviations (SD) or medians and interquartile ranges (IQR); continuous outcomes will be compared using Student's Paired t test for single group comparison. Two-tailed tests using a significance threshold of $p < 0.05$ will be used for all tests. Goal attainment will be summarized by proportion of patients who achieve their identified goals based on the set time bound duration of the goal (i.e., GAS Score ≥ 50).^{29,30} The goal attainment scale adapted for depression yields a norm-based score (standardized to a mean of 50, SD of 10) at baseline and at the end of the time bound goal; the change from score from baseline will also be summarized.

System level performance: Process outcomes will be evaluated at the system level (all primary

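### The two-cohort comparisons are sized and tested as if patients were independent; if clinics change by different amounts, the nominal 5% chi-square test is anti-conservative

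*Combined protocol and SAP*

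**What the plan says.** All references are to the combined protocol and SAP.

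- **Sample size (8.2).** The inputs are 75% before and 90% after, 80% power and a two-sided 5% level. The calculation is made "using Pearson chi square test for two independent proportions". It arrives at 100 patients in each cohort. The number is then doubled, and the reason given is not clustering: "To allow for subgroup analyses the sample will include 200 patients per group, for a total of 400 patients".
- **Analysis (8.4).** "Categorical outcomes will be presented as proportions and compared using Pearson Chi2 test". Continuous outcomes compared between cohorts use an independent-groups Student's t test. The threshold is two-sided 0.05 throughout. Nowhere is there an ICC, a design effect, a clinic term, a mixed or GEE model, or a robust variance.
- **Structure.** "The Pathway Platform will be implemented in up to 20 primary care sites" (3.1), and the pre-implementation cohort comes from the same clinics (3.2). Section 3.2 also mentions 20 patients per site, which for 200 patients would mean 10 sites.
- **Intervention.** Care-team education is given to clinic staff, and "up to three audit and feedback sessions will be conducted for each participating clinic" (4.4.3), with team action plans among their aims. The app itself is taken up by individually consenting patients (4.3).
- **Care model.** Section 8.3.3 plans a subgroup analysis by care model at site level.

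**The concern.** The primary outcome, at least two PHQ-9 scores documented over six months, is a process measure that depends partly on how a clinic works. Patients in one clinic share a care team and workflow, and feedback and action plans are made clinic by clinic. It is therefore plausible that PHQ-9 use changes more in some clinics than in others. Such clinic-by-period variation does not shrink as more patients are added within a clinic, and neither the Pearson chi-square nor the independent-groups t test carries it. Equal clinic shares in the two cohorts do not remove it.

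At stake is whether a result declared significant at 5% really has a 5% false-positive rate. The site-level care-model comparison is the most exposed, because there the clinics themselves are being contrasted.

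**Working it through.** **1. The plan's own figure.** With p1 = 0.75, p2 = 0.90, mean 0.825, two-sided alpha 0.05 and 80% power:

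n = [1.960·√(2·0.825·0.175) + 0.842·√(0.75·0.25 + 0.90·0.10)]² / 0.15² = 99.5, so 100 per group.

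The stated figure reproduces. Under independence, power is 80.2% at 100 per group and 97.9% at 200.

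**2. Design effect.** For two separate patient samples from the same clinics, with balanced clinic mix and equal clinic sizes:

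DE = 1 + (m − 1)·ICC − m·ICC·r

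Here m is patients per clinic per period, ICC the within-period intraclass correlation, and r the between-period correlation of clinic rates. The true type I error of the unadjusted test is 2·[1 − Φ(1.960/√DE)]. ICC and r are **assumptions**. With 200 per group, m = 10 for 20 clinics and m = 20 for 10 clinics.

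| ICC, r | DE, 20 clinics | Type I | DE, 10 clinics | Type I |
|---|---|---|---|---|
| 0.05, 1 (stable clinic effects only) | 0.95 | 4.4% | 0.95 | 4.4% |
| 0.05, 0.8 | 1.05 | 5.6% | 1.15 | 6.8% |
| 0.05, 0.5 | 1.20 | 7.4% | 1.45 | 10.4% |
| 0.082, 0.49 | 1.34 | 9.0% | 1.75 | 13.9% |

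Example for the third row, 10 clinics: 1 + 19·0.05 − 20·0.05·0.5 = 1.45, and 1.960/√1.45 = 1.628, giving 10.4%.

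Simulation of clustered binary data at 75% in both periods agrees. At ICC about 0.05 with 10 clinics, type I error was 4.6%, 6.8% and 10.5% for r = 1, 0.8 and 0.5. A clinic-level paired t test, simulated with equal clinic sizes, stayed at 4.5-5.2%.

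**3. Power at ICC 0.05, r = 0.5,** using the effective number n/DE.

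| Per group | Clinics | m | DE | Effective n | Power |
|---|---|---|---|---|---|
| 100 | 20 | 5 | 1.075 | 93 | 77% |
| 100 | 10 | 10 | 1.20 | 83 | 73% |
| 200 | 20 | 10 | 1.20 | 167 | 95% |
| 200 | 10 | 20 | 1.45 | 138 | 91% |

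At 200 per group the design keeps 80% power up to DE = 200/100 = 2.0. These figures use a normal reference. With only 10 clinics, a test on 9 degrees of freedom has less: the clinic-level paired t had 79-89% power over the simulated settings.

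**4. Care-model comparison.** This contrasts clinics, so the last term drops out: DE = 1 + (m − 1)·ICC. For outcomes in the post-implementation cohort at ICC 0.05, DE is 1.45 with m = 10 (type I 10.4%) and 1.95 with m = 20 (16.1%). This holds even if no clinic drifts.

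**The case against.** The best defence is that the design uses each clinic as its own comparator. Stable clinic differences cancel, and if they are the only clustering the planned test errs on the safe side. At some values, such as m = 10 with r = 0.9, DE is 1 and the test is nominal. No section reports that clinics drift differently. All of this stands, and it makes the direction and size of the error conditional. It does not make independence a justified default, since the plan offers no ICC or correlation to support it.

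Four stronger readings are tempting, and the documents do not support them:

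- *The p-values are wrong whatever happens.* They may be too large, about right or too small, depending on values not given.
- *The primary test is underpowered.* The doubling to 200 per group, though made for subgroups, absorbs DE up to 2.0. The 73-77% figure concerns the 100-per-group calculation, not the study being run. The fair complaint is that the margin meant for subgroups is partly used up.
- *The plan's confidence intervals are wrong.* It specifies none; the point applies only to intervals reported later.
- *The whole intervention is delivered to clinics, so every test is affected.* App use is individual, and the paired t and McNemar analyses within the app cohort are within-patient. They lie outside this point.

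A further fair objection concerns the remedy. An unweighted mean of clinic differences gives a clinic with few patients the same weight as one with many, so it no longer estimates the patient-level proportion in Section 8.3.1. It also loses power when enrolment is uneven, and no per-clinic quota is set for the post-implementation cohort. In a simulation with 20 clinics, power fell from 93% with equal sizes to 78-84% with uneven post-implementation enrolment; with 10 clinics it fell from 83% to 72-76%. That simulation assumed clinic and clinic-by-period standard deviations of 0.4 on the logit scale. This is why the fix below uses such an analysis only as a sensitivity check.

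**Conclusion.** The concern holds in conditional form. Sections 8.2 and 8.4 ignore clustering by clinic in the two-cohort comparisons. The unadjusted primary test has a true error of about 4.5% if clinic differences are stable. If clinics change by different amounts, it is about 6-9% with 20 clinics and 7-14% with 10. Those ranges rest on assumed ICCs of about 0.04-0.09, assumed between-period correlations of about 0.5-0.8, equal clinic sizes and balanced clinic mix. The omission is certain; its magnitude is not. Lack of power for the primary test is not shown. The care-model comparison has no cancellation to protect it and is inflated at any positive ICC, though it is an exploratory subgroup analysis. The point should be addressed before analysis and does not call for more patients.

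**What to change.** **Section 8.4, two-cohort comparisons only.** Replace the unadjusted primary test with one that keeps the patient-level proportion and carries clinic-by-period variation. Either of these would do:

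- a patient-weighted risk difference with cluster-robust variance by clinic and a small-sample correction; or
- a mixed model with clinic and clinic-by-period random effects.

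Report the risk difference with a 95% confidence interval. Add a clinic-level paired analysis as a sensitivity check. Apply the same approach to the other pre/post outcomes where numbers allow. Outcomes too sparse per clinic, such as follow-up after hospitalization or an emergency visit, may stay descriptive. Leave the within-patient paired t and McNemar analyses as they are.

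**Section 8.3.3.** Analyse the care-model subgroup with clinic as the unit.

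**Section 8.2.** State that 100 per group assumes independence. Show power at 200 per group over an assumed range of ICC and between-period correlation, for 10 and 20 clinics.

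**Cost.** Revised wording and some programming, with no new patients; clinic should be identifiable because both cohorts are drawn by clinic. The price is a somewhat wider interval and some loss of power, larger with few or unevenly sized clinics.

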8.3 Outcomes

8.3.1 Primary outcome

The primary process outcome is PHQ-9 utilization over a six-month period. For purposes of this study, PHQ-9 utilization will be defined as documentation of at least 2 PHQ-9 scores in the EMR over the initial 6-month study period. The proportion of patients who meet this definition will be compared between patients attending clinics pre- and post- implementation of the Pathway Platform. Additional analyses exploring the number of PHQ-9s over the study period will also be conducted.

8.3.2 Secondary outcome

Process outcomes: The following secondary process outcomes will be compared between patients attending clinics pre- and post- implementation of the Pathway Platform.

- Measurement- based care: The proportion of patients reflecting measurement-based care informed MDD treatment adjustments in their charts, defined as at least one dose change, medication switch, or add on medication during the study period. The frequency and types of treatment adjustments will also be explored.
- Shared- decision making: The proportion of patients reflecting shared-decision making, using the OPTION12 Tool framework.²⁶ The tool will be modified by adding a thirteenth domain inquiring about goal setting (Asking the patient or caregiver about goals of treatment). The frequency and domains of shared-decision making will also be explored in a manual chart review and a variable added to assess if the clinician documented asking the patient about their goals of treatment.
- Referrals to behavioral health: The proportion of patients with at least one referral will be compared. The frequency and types of referrals will also be explored.
- Follow-up after hospitalization for mental illness: The proportion of hospitalized adults who receive follow-up within 7 days of discharge and within 30 days of discharge.
- Follow-up after emergency department visit for mental illness: The proportion of adults

who receive follow-up within 7 days of discharge and within 30 days of ED visit.

- Healthcare resource utilization: Number and costs associated with hospital admission, length of stay, emergency room admissions, and encounters with outpatient clinics. Costs will be calculated using USA national average costs for inpatient and outpatient visits or using an average Advocate Health Care system cost.

Patient clinical outcomes: The following outcomes will be compared between patients attending clinics pre- and post- implementation of the Pathway Platform, keeping in mind that the number of patients with these measures in the pre- implementation patient group will be limited:

- MDD remission: The proportion of patients with PHQ-9 ≤ 5 at the end of the study period. The last measurement available during the study period will be used to calculate remission.
- MDD response: The proportion of patients with a 50% or greater reduction in PHQ-9 scores. The first and last scores available during the study period will be used to calculate response.
- Diagnosis progress notes stating change from mild, moderate, or severe, to in remission or partial remission will be assessed descriptively.

Patient reported outcomes: The difference in scores between baseline, and 6-month follow up will be compared among patients using the Pathway Platform who completed the following measures:

- PAM-13
- CollaboRATE (this questionnaire is also included as a 3-month post-enrollment assessment and will be analyzed across all available time points)
- WSAS

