4.1 Inclusion

1. Adult aged 18 and above

2. Diagnosis with major depressive disorder or reference to “clinical depression” in patient charts. See **Appendix 1** for ICD codes for major depressive disorders
3. Recently prescribed monotherapy antidepressant medication (defined as new start, medication switch, or dose change in the past 3 months (**Appendix 2**).
4. Patients with inadequate response or tolerability concerns determined based on A PHQ-2 score of 3 or greater, or a PHQ-2 <3 with a PHQ-9 score of 5 or greater recorded in medical records in the past 6 weeks or during screening,
5. Able and willing to provide informed consent
6. Able to use the Pathway Platform based on clinician’s judgment, e.g. owns an iPhone version 5 or later or smartphones with Android operating systems, have an active data plan or regular WiFi access.

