3.3 Study Duration

Patients will be enrolled in the study for a minimum duration of 6 months with the option to continue using the app at that time to a common study end date of January 7, 2023 (access to in-app final study evaluations will end January 21, 2023). Data from the Pathway Platform will be collected prospectively for the duration of the patient's participation. Process measures will be collected retrospectively from the EMR and through manual chart review after 6 months of enrollment and at the end of the study(post-implementation) and over a 6-month period prior to implementation (pre-implementation).

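### A switch or dose change that admits a patient also meets the treatment-adjustment outcome, and the plan gives conflicting counting windows, so the entry event may be scored in neither, one or both cohorts

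*Combined protocol and SAP*

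**What the plan says.** Entry (section 4.1, criterion 3): "Recently prescribed monotherapy antidepressant medication (defined as new start, medication switch, or dose change in the past 3 months".

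Outcome (section 8.3.2, first process outcome): the proportion of patients with a treatment adjustment, "defined as at least one dose change, medication switch, or add on medication during the study period". The cohorts are compared by Pearson chi-square at two-sided 0.05 (section 8.4). Section 8.3.2 does not say when the study period starts or ends for this outcome. The primary outcome in section 8.3.1, by contrast, is limited to the initial six months.

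Post-implementation window:
- Section 5.2: "For the post-implementation cohort, data will be collected from the time of study implementation until the end of the study".
- The note to Figure 1 has secondary outcomes evaluated at 6 months, with later data kept for exploration.
- Section 3.3 (Study Duration) has process measures collected once 6 months of enrollment have passed and again at study end.

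Pre-implementation window:
- Section 5.2: "For the pre-implementation cohort, data will be collected over a six-month period", with no starting point.
- Section 3.2: "Patient history will be evaluated for three months prior to index visit to confirm eligibility". It describes the entry event sought as "new start, dose adjustment or switch of an antidepressant medication 6 months prior to the implementation index date (three-month inclusion window for patient identification"), and then has six months of history collected.
- Section 3.3 (Study Duration): "over a 6-month period prior to implementation (pre-implementation").

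**The concern.** This outcome is meant to show whether care teams adjust treatment more often once the platform is in use. A switch or dose change made before or at entry says nothing about that, because it is the reason the patient is in the cohort. If such changes are counted, the proportion mixes later clinical practice with the way patients were selected. If they are counted to different extents in the two cohorts, the test can reject, or fail to reject, because of the window alone.

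The outcome's label refers to adjustments informed by measurement. The operational definition that follows requires no link to a PHQ-9 score, so the label does not screen out the entry event.

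**Working it through.** **Step 1. Overlap.** Entry events are new start, switch and dose change. Outcome events are dose change, switch and add-on. Switch and dose change are in both lists; a new start is not an outcome event. The overlap covers two of three entry routes, and the documents do not give the mix.

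**Step 2. What each window does to a change made before entry.**
- *Neither cohort.* Both windows start at the index or enrollment visit. The change lies outside both unless it was made on that day.
- *Post only.* Section 5.2 is taken literally for the post cohort and the pre window starts at index. A patient switched 5 weeks before onboarding, but after implementation, and not changed again, is a success in the post cohort. The same history in the pre cohort is a failure.
- *Pre only.* The post window starts at enrollment. The pre window is read from section 3.3 (Study Duration) as the 6 months before implementation, together with the loosely placed entry event in section 3.2, so that some pre-cohort entry events fall inside it.
- *Both.* Both windows reach back over the entry event.

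**Step 3. The plan's own figure.** Section 8.2 gives a sample size for the primary outcome only: 75% versus 90%, 80% power, two-sided 0.05, 100 per group. The pooled-variance formula is n = [1.960·√(2·p̄·(1−p̄)) + 0.842·√(p1(1−p1)+p2(1−p2))]² / (p2−p1)². With p̄ = 0.825 this is (1.053 + 0.443)² / 0.0225 = 99.5, so 100. The figure reproduces, and the same variance convention is used below with the planned 200 per cohort.

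**Step 4. Model (all rates assumed).** Let r be the true rate of adjustment after entry, q the share of entry events that are a switch or dose change, and c the share of those falling inside the window. Then g = q·c is the share of patients whose entry event is counted, and observed rate = r + (1−r)·g.

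The chance of p<0.05 is Φ((|d| − 1.96·SE0)/SE1) plus a negligible opposite tail when d is not near zero. Here d is the observed difference, SE0 = √(2·p̄(1−p̄)/200) and SE1 = √((p1(1−p1)+p2(1−p2))/200).

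**Step 5. Capture in the post cohort only, no true effect, r = 40%.**
- g = 10%: 0.40 + 0.60×0.10 = 46% versus 40%. (0.06 − 0.0970)/0.0494 = −0.75, giving about 23%.
- g = 25%: 0.40 + 0.60×0.25 = 55% versus 40%. (0.15 − 0.0979)/0.0494 = 1.06, giving about 85%.
- At g = 25%, true rates of 50% and 30% give spurious gaps of 0.50×0.25 = 12.5 points and 0.70×0.25 = 17.5 points.

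To see whether such g are plausible under section 5.2 taken literally, assume enrollment uniform over T months from implementation and the change uniform over the 3 months before enrollment. Then c = 1 − 1.5/T for T ≥ 3, which is 50% at T = 3 and 75% at T = 6. With q = 25% and c = 75%, g = 18.75%, the observed rates are 51.2% versus 40%, and the chance of p<0.05 is 62%.

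**Step 6. Capture in both cohorts (c = 1), true 40% versus 55%.**

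| q | Pre | Post | Difference (points) | Power |
|---|---|---|---|---|
| 0 | 40.0% | 55.0% | 15.0 | 85% |
| 25% | 55.0% | 66.3% | 11.3 | 64% |
| 50% | 70.0% | 77.5% | 7.5 | 40% |

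**Step 7. Capture in the pre cohort only (c = 1), true 40% versus 55%.** At q = 25% the observed rates are 55% versus 55%, and the gain disappears. At q = 50% they are 70% versus 55%, and the sign reverses.

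**Step 8. Capture in neither (c = 0).** With equal true rates the rejection probability is 5.0%, and power for 40% versus 55% is 85%.

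**The case against.** The strongest reply is that section 5.2 states how long chart data are collected, not which part is scored. Several places tie the outcome period to the patient: the Figure 1 note, the six-month enrollment in section 3.1, section 3.3 (Study Duration), and the schedule footnote that ends the initial 24-week period at Day 168. If the study period in section 8.3.2 means those six months from enrollment, a switch 5 weeks before onboarding is outside it and the comparison is unharmed.

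This stands as far as it goes. A reader might infer from section 5.2 that the cohorts do capture the entry event unequally and that the bias favors the platform. The documents do not support that. It is one literal reading, other passages point away from it, and the pre window is itself described from two different origins, so even the direction is open. Nor does every eligible patient enter with an outcome event, because new starts do not count.

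The reply does not close the point. The passages it relies on say when outcomes are evaluated or data collected. None says that counting begins at enrollment for this outcome or that the qualifying change is left out. A change made on the index or enrollment day is unresolved even under the favorable reading. Equal windows are not enough either: if both include the entry event, Step 6 applies.

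**Conclusion.** The concern holds as an overlap of definitions combined with conflicting windows. A qualifying switch or dose change meets the outcome definition, no rule excludes it, and an analyst could follow any of the stated windows. The result could be unaffected, diluted, inflated or masked.

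The documents give no adjustment rate, mix of entry events or length of enrollment, so the sizes are illustrations. One-sided capture in 10% to 25% of patients, at a 40% true rate in both cohorts, takes a nominal 5% error rate to about 23% to 85%. Full capture in both, with 25% to 50% of entry events being switches or dose changes, takes power for 40% versus 55% from about 85% to 64% or 40%. The existence of the conflict rests on the text alone; only its size depends on these assumptions. The point concerns a tested secondary outcome, not the primary endpoint.

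**What to change.** - In section 8.3.2, define the study period for this outcome as the same 6 months in both cohorts, running from the index visit (pre) or the enrollment visit (post).
- State that the specific change used to satisfy inclusion 3 never counts, including when it is made on the index or enrollment day.
- For a patient already qualified by an earlier change who has a separate adjustment on that day, state one rule and apply it identically in both cohorts.
- Reconcile sections 3.2, 3.3 (Study Duration) and 5.2 with this window. Section 5.2 can keep the longer extraction period if it says that only the common window is scored.
- Tabulate the type of qualifying event (new start, switch, dose change) by cohort.

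The cost is a few sentences and one table. Applying inclusion 3 already requires medication changes to be dated. The downside is that the reported adjustment proportions will be lower in any cohort where entry events would otherwise have been counted.
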